5.10.2.2. Sensitivity Analyses

The sensitivity analyses described in [Section 5.9.3](#) for the primary estimand will also be performed for the secondary efficacy estimand 2 except for the sensitivity analyses to assess the impact of missing value handling. For the secondary efficacy estimand 2, the case of potential MNAR will be imputed as “non-responder” for the sensitivity analysis. No additional sensitivity analysis under the MAR assumption using multiple imputations will be performed. In addition, a sensitivity analysis excluding the PGIC score obtained remotely may be performed if such remote assessments are conducted due to COVID-19 restrictions.

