5.9.3.4. Impact of Missing Values Handling

Whilst every effort will be made to prevent avoidable missing values during the study conduct ([National Research Council, 2010](#)), it is unrealistic to expect no missing values in clinical trials. The impact of missing values on the analysis results will be assessed by the sensitivity analyses described below.

Under Missing at Random (MAR) Assumption

Multiple imputation (MI) will be performed to replace each missing value with a set of plausible values that represent the uncertainty about the correct value to impute. The Markov chain (MCMC) method will be utilized for the mITT set. SAS PROC MI will be used to generate 27 possible imputed datasets: Each of these datasets will be analyzed using PROC MIXED in SAS using the MMRM model as described in [Section 5.9.2](#). The results of the analyses of the datasets will be combined using PROC MIANALYZE to produce an inferential result.

Considerations of Data Potentially Missing Not at Random (MNAR)

A pattern mixture model (PMM) approach will be used to address potentially MNAR patterns. The following three patterns of subjects in the mITT set will be considered:

- 1) Subjects with no missing values from discontinuation or from initiation of prohibited Parkinson's disease concomitant mediation during treatment period.
- 2) Subjects with missing values from the types of ICEs below will be considered having MNAR
 - a. Subjects who discontinue due to reasons, as recorded on the eCRF, of lack of efficacy, adverse events associated with motor symptoms of Parkinson's disease, physician decision, and withdrawal by subject.
 - b. Subjects who initiated concomitant Parkinson's disease medications (ATC classifications of ADAMANTANE DERIVATIVES, DOPAMINE AGONISTS, MONOAMINE OXIDASE B INHIBITORS, OTHER ANTI-PARKINSON DRUGS, OTHER DOPAMINERGIC AGENTS, or DOPA AND DOPA DERIVATIVES) after the first dose of IMP and prior to the last dose of IMP with a use duration of 7 days or more will be considered having a potential confounding ICE. The efficacy data post ICE will be treated as missing with the missing pattern of MNAR.

The MNAR cases will be identified and documented prior to database lock and unblinding ([Section 9.5](#)).

- 3) Subjects with missing values from the type of ICEs below will be considered as having MAR

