 - a. Missing values after discontinuation due to reasons, as recorded on the eCRF, of death, pregnancy, loss to follow-up, adverse event unrelated to motor symptoms of Parkinson's disease, non-compliance, site termination, protocol deviation, failure to meet continuation criteria and other will be considered as MAR.

The MNAR pattern 2) above in the active treatment group will be imputed using the jump to reference (J2R) method (Cro et. al. 2020) by assuming that patients jump to behave like those in the placebo group following their last observed time point. However, such MNAR in the placebo group will still be imputed as MAR using the standard multiple imputation method.

The MAR patterns 3) will be imputed using the standard multiple imputation method described above.

Other missing values due to missed visits/assessments before endpoint or discontinuation will also be assumed as MAR and imputed using the standard multiple imputation method for all three patterns.

Core codes for MAR and MNAR imputations are provided in [Section 9.6](#).

Under Missing Completely at Random (MCAR) Assumption

An additional sensitivity analysis will be conducted on the Endpoint (Week 26) Completer set using the MMRM analysis method described in [Section 5.9.2](#).

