5.10.1.2. Sensitivity Analyses

The sensitivity analyses described in [Section 5.9.3](#) for the primary estimand will also be performed for the secondary efficacy estimand 1.

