Hypothetical strategy with data after treatment discontinuations or after the start of prohibited concomitant medications censored	
 • mITT population • Treatment as randomized • GLIMMIX model described in Section 5.10.2.1 	
 • Treatment effect at final dose levels • Treatment effect based on actual treatment received, if applicable • Potential MNAR missing values treated as non-responders • Endpoint completer analysis • Analysis with remote assessments excluded (treated as missing) 	
 • Age • Sex • Hoehn&Yahr Status • MAO-B inhibitor use • Baseline MDS-UPDRS Part II and Part III baseline • Years since diagnosis • Race • Region

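### The only MNAR sensitivity analysis for PGIC sets potential-MNAR subjects to non-responder in every arm, so it can favour tavapadon if such cases are more frequent on placebo

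*SAP*

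**What the plan says.** SAP 5.9.3.4 sorts subjects into missing-data patterns without regard to arm: "The following three patterns of subjects in the mITT set will be considered". Pattern 2, potentially MNAR, covers discontinuation for lack of efficacy, motor-symptom adverse events, physician decision or withdrawal by the subject. It also covers anyone who starts Parkinson's medication on treatment and uses it for at least 7 days. Other discontinuations, including those for adverse events unrelated to motor symptoms, are classed as MAR.

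For Parts II+III combined the two kinds of arm are handled differently. On active: "The MNAR pattern 2) above in the active treatment group will be imputed using the jump to reference (J2R) method". On placebo: "However, such MNAR in the placebo group will still be imputed as MAR using the standard multiple imputation method". SAP 5.10.1.2 carries this over to Part II; the analyses set out "for the primary estimand will also be performed for the secondary efficacy estimand 1".

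For PGIC, SAP 5.10.2.2 adopts the primary endpoint's sensitivity analyses "except for the sensitivity analyses to assess the impact of missing value handling". In their place: "For the secondary efficacy estimand 2, the case of potential MNAR will be imputed as" non-responder. The 5.11 table repeats the rule: "Potential MNAR missing values treated as non-responders". No arm is named or exempted in either place, and nothing brings the placebo-at-MAR rule across. Multiple imputation under MAR is dropped for PGIC. SAP 5.10.2.1 assumes MAR in the main model and says that sensitivity analyses will examine departures from it.

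**The concern.** Non-responder imputation is the only MNAR analysis behind H4 and H6. The other missing-data check listed for PGIC in 5.11 is the completer analysis, which 5.9.3.4 places under MCAR, a stronger assumption than MAR. A sensitivity analysis of this kind is useful if it puts the main result under strain. Setting placebo subjects to failure lowers the placebo response rate. If pattern 2 is commoner on placebo, that loss can outweigh the loss on active and the odds ratio rises.

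A placebo excess is plausible. Protocol 5.1 criterion 9 admits only subjects judged to need drug treatment, and Protocol 7.3 lists worsening that calls for added Parkinson's medication as a reason to stop. Pattern 2 contains lack of efficacy and medication start. Adverse events unrelated to motor symptoms, which would take in the nausea and vomiting named in Protocol 2.3 among the commonest reasons for stopping tavapadon, fall under MAR. In that case a favourable PGIC check could be cited as support for robustness that it had not tested.

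**Working it through.** **Inputs.** The plan states no PGIC response rate, PGIC power or pattern-2 share, so there is no figure to reproduce. The imputation rules and the odds-ratio measure at Week 26 come from SAP 5.9.3.4, 5.10.2 and 5.10.2.2. Assumed: MAR response pA = 40% on active and pP = 25% on placebo, with pattern-2 shares mA and mP varied.

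**Formulas**, with odds(p) = p/(1−p):
- MAR: odds(pA) / odds(pP)
- Rule as written: odds(pA(1−mA)) / odds(pP(1−mP))
- Jump-to-reference analogue, placebo at MAR: odds(pA(1−mA) + pP·mA) / odds(pP)
- Active-only non-responder: odds(pA(1−mA)) / odds(pP)

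**mA = 8%, mP = 20%:**
- MAR: (0.40/0.60) / (0.25/0.75) = 0.667/0.333 = 2.00
- As written: 0.40×0.92 = 0.368 and 0.25×0.80 = 0.200; 0.582/0.250 = 2.33
- Jump-to-reference analogue: 0.368 + 0.25×0.08 = 0.388; 0.634/0.333 = 1.90
- Active-only non-responder: 0.582/0.333 = 1.75

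**Other shares, same response rates (MAR 2.00):**

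| mA / mP | As written | Jump-to-reference analogue |
|---|---|---|
| 8% / 15% | 2.16 | 1.90 |
| 10% / 15% | 2.08 | 1.88 |
| 10% / 10% | 1.94 | 1.88 |
| 15% / 15% | 1.91 | 1.82 |
| 20% / 10% | 1.62 | 1.76 |

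**Crossover.** With mA = 8%, the written rule returns 2.00 when the placebo odds equal 0.582/2 = 0.291. That is a rate of 0.291/1.291 = 0.2255, so mP = 1 − 0.2255/0.25 = 9.8%. With mA = 10%, the crossover in mP is 11.3% for response rates of 30% vs 20%, 12.2% for 40% vs 25%, 13.5% for 50% vs 30% and 14.3% for 60% vs 40%. A placebo excess of about 1 to 4 percentage points is enough.

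**No true effect.** With 30% response in both arms and 8%/20% shares, the written rule compares 27.6% with 24.0%: 0.381/0.316 = 1.21. The jump-to-reference analogue stays at 1.00. With 174 per arm, the log odds ratio is 0.188 and its standard error √(1/(174×0.276×0.724) + 1/(174×0.24×0.76)) = 0.2455. The chance of a nominal two-sided p<0.05 favouring tavapadon is the upper tail beyond 1.96 − 0.188/0.2455 = 1.19, about 12% instead of 2.5%.

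**Limit of the method.** This is a marginal approximation, not a GLIMMIX fit. It lets pattern-2 subjects count at their arm's overall rate under MAR. A repeated-measures model uses earlier visits, so subjects already doing poorly would count at a lower rate, and setting them to non-responder would then move each arm less.

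**The case against.** Counting a subject who stops for lack of efficacy or starts Parkinson's medication as a non-responder is a coherent and conventional departure from MAR for a binary endpoint. It treats the arms alike, can be applied to cases fixed before unblinding, and was an express choice: 5.10.2.2 excepts PGIC from the MDS-UPDRS rules. SAP 5.10.2.1 promises an assessment of departures from MAR, not one that must lower the odds ratio. All of this stands, and it is why the both-arm run should be kept.

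The direction is also uncertain. Pattern 2 includes subject withdrawal, physician decision and motor adverse events, and Protocol 2.3 lists dyskinesia, falls and tremors among the common reasons for stopping tavapadon. These could load the pattern onto active. The cases are to be documented in SAP 9.5, but its content was not available for this review.

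A reader might draw four stronger conclusions that the documents do not support:
- That the check is biased towards tavapadon. No case counts by arm are available, and with equal or heavier active shares the check is conservative.
- That all placebo dropouts become failures. Only pattern 2 does; loss to follow-up, non-compliance, non-motor adverse events and the other listed reasons stay at MAR.
- That false-positive risk for H4 or H6 rises to 12%. Those tests use the MAR model. The 12% concerns a supportive run and assumes a large placebo excess alongside no drug effect, which is a strained combination.
- That 5.9.3.4 implies the value 1.75. It specifies jump to reference, whose analogue is 1.90. Active-only failure imputation is harsher than anything in the SAP and falls below 1 when the true rates are equal.

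**Conclusion.** The difference between endpoints is in the text, and its consequence is conditional. When pattern 2 is more frequent on placebo by a modest margin, the PGIC check gives a larger odds ratio than the analysis it is meant to test: 2.33 against 2.00 under the assumed 40% vs 25% response and 8% vs 20% shares. A jump-to-reference analogue with placebo at MAR stays below the MAR value whatever the placebo share, as long as active response exceeds placebo response. The result depends on assumed response rates and shares, and on reading the absence of an arm limit in 5.10.2.2 and 5.11 as covering placebo. The confirmatory testing sequence is untouched. This is an inexpensive improvement to a supportive analysis of a key secondary endpoint.

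**What to change.** In SAP 5.10.2.2 and 5.11:
- Keep non-responder imputation and state that it applies to all arms.
- Add one sensitivity row in which tavapadon pattern-2 subjects are imputed from the placebo response rate and placebo pattern-2 subjects stay at MAR, matching 5.9.3.4.
- Report pattern-2 counts by arm, so that a reader can see which way the both-arm rule pushes.

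Cost: a reference-based imputation for a binary outcome has to be programmed. The code in SAP 9.6.2 feeds a continuous MMRM, and no multiple imputation is currently planned for PGIC, so this is more than a wording change. The added odds ratio may be less favourable than the both-arm one. The pattern-2 cases are already to be identified before database lock, so no new data are needed.

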5.10.2.3. Subgroup Analyses

The subgroup analyses described in [Section 5.9.4](#) for the primary estimand will also be performed for the secondary efficacy estimand 2: proportion of responders at Week 26.

5.11. Summary of Primary and Key Secondary Efficacy Analyses

ICE Strategy	Primary Analysis	Sensitivity Analysis	Subgroup Analysis
Primary Endpoint: Change from baseline in the MDS UPDRS Part II + III combined score at Week 26			
Hypothetical strategy with data after treatment discontinuations or after the start of prohibited concomitant medications censored	
 • mITT population • Treatment as randomized • MMRM described in Section 5.9.2 	
 • Treatment effect at final dose levels • Treatment effect based on actual treatment received, if applicable • Missing values imputation using multiple imputations (MI) • Missing values imputation using pattern mixture model (PMM) • Endpoint completer analysis • Analysis with remote assessments excluded (treated as missing) 	
 • Age • Sex • Hoehn&Yahr Status • MAO-B inhibitor use • Baseline MDS-UPDRS Part II and Part III baseline • Years since diagnosis • Race • Region
Key Secondary Endpoint 1: Change from baseline in the MDS UPDRS Part II score at Week 26			
Hypothetical strategy with data after treatment discontinuations or after the start of prohibited concomitant medications censored	
 • mITT population • Treatment as randomized • MMRM described in Section 5.9.2 	
 • Treatment effect at final dose levels • Treatment effect based on actual treatment received, if applicable • Missing values imputation using multiple imputations (MI) • Missing values imputation using pattern mixture model (PMM) • Endpoint completer analysis • Analysis with remote assessments excluded (treated as missing) 	
 • Age • Sex • Hoehn&Yahr Status • MAO-B inhibitor use • Baseline MDS-UPDRS Part II and Part III baseline • Years since diagnosis • Race • Region
Key Secondary Endpoint 2: Proportion of PGIC responders at Week 26			
Hypothetical strategy with data after treatment discontinuations or after the start of prohibited concomitant medications censored	
 • mITT population • Treatment as randomized • GLIMMIX model described in Section 5.10.2.1 	
 • Treatment effect at final dose levels • Treatment effect based on actual treatment received, if applicable • Potential MNAR missing values treated as non-responders • Endpoint completer analysis • Analysis with remote assessments excluded (treated as missing) 	
 • Age • Sex • Hoehn&Yahr Status • MAO-B inhibitor use • Baseline MDS-UPDRS Part II and Part III baseline • Years since diagnosis • Race • Region

5.12. Other Efficacy Analyses

Endpoint	Analysis Population	ICE Strategy	Analysis Method	Subgroup Analysis
Secondary Endpoints				
Change from baseline in the MDS UPDRS Part II + III combined score (all time points)	mITT	Hypothetical	MMRM described in Section 5.9.2	
 • Age • Sex • Hoehn&Yahr Status • MAO-B inhibitor use • Baseline MDS-UPDRS Part II and Part III baseline • Years since diagnosis • Race • Region
Change from baseline in the MDS UPDRS Part I, Part II, and Part III combined score (all time points)	mITT	Hypothetical	MMRM described in Section 5.9.2	
 • Age • Sex • Hoehn&Yahr Status • MAO-B inhibitor use • Baseline MDS-UPDRS Part II and Part III baseline • Years since diagnosis • Race • Region
Change from baseline in the MDS UPDRS Part I score (all time points)	mITT	Hypothetical	MMRM described in Section 5.9.2	
 • Age • Sex • Hoehn&Yahr Status • MAO-B inhibitor use • Baseline MDS-UPDRS Part II and Part III baseline • Years since diagnosis • Race • Region
Change from baseline in the MDS UPDRS Part II score (all time points)	mITT	Hypothetical	MMRM described in Section 5.9.2	
 • Age • Sex • Hoehn&Yahr Status • MAO-B inhibitor use • Baseline MDS-UPDRS Part II and Part III baseline • Years since diagnosis • Race • Region

Endpoint	Analysis Population	ICE Strategy	Analysis Method	Subgroup Analysis
Change from baseline in the MDS UPDRS Part III score (all time points)	mITT	Hypothetical	MMRM described in Section 5.9.2	
 • Age • Sex • Hoehn&Yahr Status • MAO-B inhibitor use • Baseline MDS-UPDRS Part II and Part III baseline • Years since diagnosis • Race • Region
Change from baseline in the CGI-S score (all time points)	mITT	Hypothetical	MMRM described in Section 5.9.2	
 • Age • Sex • Hoehn&Yahr Status • MAO-B inhibitor use • Baseline MDS-UPDRS Part II and Part III baseline • Years since diagnosis • Race • Region
CGI-I score (all time points)	mITT	Hypothetical	MMRM described in Section 5.9.2	
 • Age • Sex • Hoehn&Yahr Status • MAO-B inhibitor use • Baseline MDS-UPDRS Part II and Part III baseline • Years since diagnosis • Race • Region
PGIC score (all time points)	mITT	Hypothetical	MMRM described in Section 5.9.2	
 • Age • Sex • Hoehn&Yahr Status • MAO-B inhibitor use • Baseline MDS-UPDRS Part II and Part III baseline • Years since diagnosis • Race • Region

Endpoint	Analysis Population	ICE Strategy	Analysis Method	Subgroup Analysis
Other Endpoints				
Change from baseline in the PDQ 39 score	mITT	Hypothetical	MMRM described in Section 5.9.2	None
Change from baseline in the Schwab and England ADL score	mITT	Hypothetical	MMRM described in Section 5.9.2	None
Change from baseline in the EQ-5D-5L index score	mITT	Hypothetical	MMRM described in Section 5.9.2	None
Change from baseline in EQ-5D-5L VAS score	mITT	Hypothetical	MMRM described in Section 5.9.2	None

Cohen's D effect size by time point will be derived for MDS-UPDRS Part II+III and MDS-UPDRS Part II only. Time curve plots will be presented for LSMean (SE) of change from baseline for MDS-UPDRS Part II+III, Part I+II+III, individual Part I, II and III, CGI-S, and Schwab and England ADL scores as well as for LSMean (SE) of CGI-I and PGIC over time.

5.13. Interim and Final Analysis

A final analysis will be conducted once the last subject completes or discontinues the study, and the resulting clinical database has been cleaned, quality checked, and the database has been locked.

No interim analysis is planned.

5.14. Safety Analyses

All safety analyses will be performed on the full analysis set (FAS). Should any subjects receive a treatment other than their randomized treatment, the treatment as received will be used in the safety presentation.

5.14.1. Adverse Events

Adverse events will be mapped to a Medical Dictionary for Regulatory Activities (MedDRA) version 27.0 or higher preferred term and system organ class. If a subject experiences multiple events that map to a single preferred term, the greatest severity and strongest investigator assessment of relation to IMP will be assigned to the preferred term for the appropriate summaries. Events with missing severity or relationship will be classified as outlined in [Section 3.2](#). Missing onset dates will be imputed as previously outlined in [Section 4.1](#) as required to determine treatment-emergent events.

Summaries of treatment-emergent AEs will include any AEs reported beginning with the initiation of study drug on Day 1 through end of reporting period specified in the protocol post the last dose of IMP. The occurrence of TEAEs will be summarized by treatment group using preferred terms, system organ classes, and severity. The TEAEs by subgroup of MAO-B inhibitor use will be summarized by treatment, organ class, and preferred term. Separate summaries of treatment-emergent serious adverse events (TESAEs), TEAEs related to IMP, AESIs (including AEs related to abuse potential and AEs involving medication handling irregularities), events leading to the discontinuation of IMP, and AESIs that did not result in discontinuation of IMP or study will be generated respectively. A summary of AEs by treatment phase and by dose at event onset will also be presented. Adverse events leading to the discontinuation of IMP by preferred term and phase at onset will be prepared. All adverse events reported will be listed for individual subjects showing both verbatim and preferred terms. All adverse events that occurred prior to the initiation of study treatment or after the protocol-specified reporting period post the last dose of IMP will be excluded from the summary tables but will be included in the listings.

In addition, TEAEs rate per 100 person-years of exposure (PYE) will be summarized by treatment group using system organ class and preferred term. TEAEs with $\geq 2\%$ incidence in either tavapadon dose group and a greater incidence than the placebo group will be summarized by treatment group using preferred term in descending order of the incidence in the tavapadon 15 mg group followed by that in the tavapadon 5 mg group. The most common TEAEs, defined as an incidence $\geq 5\%$ in either tavapadon dose group and greater than 2 times of the incidence in the placebo group, will also be summarized by treatment group using preferred term in descending order of the incidence in the tavapadon 15 mg group followed by that in the tavapadon 5 mg group.

5.14.2. Epworth Sleepiness Scale (ESS)

The ESS individual questions and total score and corresponding changes from baseline will be summarized by treatment group and study visit. The percentage of subjects with sleepy (10 or more) and very sleepy (18 or more) scores will also be summarized. ESS individual question score as well as the total score will be presented in a listing. The ESS total score will also be analyzed using the same method (MMRM analysis) described in [Section 5.9.2](#) to explore any treatment difference in sleepiness. Time curve plot will be presented for LSMean (SE) of change from baseline.

5.14.3. Questionnaire for Impulsive-Compulsive Disorders in Parkinson Disease Rating Scale (QUIP-RS)

The QUIP-RS component scores (Gambling, Sex, Buying, Eating, Hobbyism-Punding, PD Medication Use), total ICD score, and total score and corresponding changes from baseline will be summarized by treatment group and study visit. QUIP-RS individual data will be presented in a listing. The total ICD score will also be analyzed using the same method (MMRM analysis) described in [Section 5.9.2](#) to explore any treatment difference in impulsive-compulsive behaviors. Time curve plots will be presented for LSMean (SE) of change from baseline.

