2 INTRODUCTION

2.1 Trial Rationale

Tavapadon (PF-06649751, CVL-751) is a partial agonist of the dopamine D1-like receptors (D1Rs), with high specificity for the D1 and D5 receptor subtypes (D1/D5), which is being developed as a treatment for Parkinson's disease (PD). Efforts to develop selective D1R agonists have been ongoing for decades, in part, because of their clear potential to produce robust efficacy through selective stimulation of the direct pathway. Mechanistic evidence also suggests that selective and partial activation of D1Rs may avoid some of the limiting side effects of the D2/3 agonist or dopamine replacement therapies.

The efficacy, safety, and tolerability of tavapadon in Phase 1b and 2 trials support its potential as the first partial agonist therapy in an important new dopamine receptor-selective mechanism for treatment of PD symptoms. By targeting the D1R subtype, tavapadon aims to improve motor control symptoms while minimizing adverse events (AEs) that may be mechanistically linked to D2/D3 dopamine receptor agonists (notably, dose-limiting hypotension, impulse control disorders, sleep disorders, and, potentially, some forms of hallucinations).

This prospective, Phase 3, multicenter, multinational, randomized, double-blind, placebo-controlled, parallel-group, 27-week trial will evaluate the efficacy, safety, tolerability and pharmacokinetics (PK) of 2 fixed doses of tavapadon (5 mg and 15 mg once daily [QD]) in subjects with early PD to further define and confirm the magnitude of efficacy and the risk/benefit profile of this specific target dose range. A substudy is also included in the main trial to characterize the relationship between tavapadon concentrations and the QT interval.

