9.4.2 Safety Analyses

All safety analyses (Table 10) will be performed on the full analysis set (FAS). Should any subjects receive a treatment other than their randomized treatment, the treatment as received will be used in the safety presentation.

Table 10 Safety Analysis

Endpoint	Statistical Analysis Methods
TEAEs, including abuse-related AEs and AEs related to MHIs	TEAEs will be coded according to MedDRA and summarized by treatment group, system organ class, and preferred term. Additional summaries by seriousness, severity, relationship to IMP, and dose at the time of onset will also be prepared.
Other safety	The C-SSRS, ESS, QUIP-RS, laboratory data, vital sign data, and ECG data will be summarized with descriptive statistics.

Abbreviations: AE = adverse events, C-SSRS = Columbia-Suicide Severity Rating Scale, ECG = electrocardiogram, ESS = Epworth Sleepiness Scale, IMP = investigational medicinal product, MedDRA = Medical Dictionary for Regulatory Activities, MHIs = medication handling irregularities, QUIP-RS = Questionnaire for Impulsive-Compulsive Disorders – Rating Scale, TEAE = treatment-emergent adverse event.

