3.2.2. Epworth Sleepiness Scale (ESS) Total Score

The ESS scale is used to determine the level of daytime sleepiness. There are 8 situations listed for which patients rate their likelihood of dozing or sleeping (0=no chance of dozing, 1=slight chance of dozing, 2=moderate chance of dozing, or 3=high chance of dozing). The total score is the sum of 8 item scores and can range between 0 and 24. The higher total score indicates the higher level of daytime sleepiness. A score of 10 or more is considered sleepy, and a score of 18 or more is very sleepy.

In case of missing item scores from the ESS, the missing value will be replaced by the average of non-missing scores at the same visit from the same subject. In case all item scores are missing, the total score will be set as missing.

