5.14.5. Clinical Laboratory Assessments

Descriptive summaries of selected (quantitative) clinical laboratory results will be presented by treatment group and study visit. Laboratory values outside the normal range for each systematically collected hematology, blood chemistry, and urinalysis parameter will be identified. Each subject's hematology, blood chemistry, and quantitative urinalysis values will be flagged as "low" (below the lower limit of normal/LLN), "normal" (within the normal range), or "high" (above the upper limit of normal/ULN) relative to the normal ranges of the central laboratory. Each subject's qualitative urinalysis results will be flagged as "normal" or "abnormal". In addition, the severity of laboratory abnormality will be graded based on toxicity criteria specified in [Section 9.8](#) in reference to Common Terminology Criteria for Adverse Events (CTCAE) Version 5.0. The result of each laboratory test for individual subjects will be presented in a listing with the normal range defined by the central laboratory, the status relative to the normal range, and the toxicity grade.

Shift table will be used to summarize shifts from baseline toxicity grades to greatest (worst) treatment-emergent laboratory toxicity grade. For hematology and, blood chemistry, and quantitative urinalysis parameters that toxicity grade was not defined, a shift table for each laboratory test will be based on the shift from baseline high/normal/low status to the status of the maximum post-baseline value and the minimum post-baseline value (including test results from unscheduled visits, if any). Similarly, for qualitative urinalysis parameters, shifts from baseline normal/abnormal status to the worst post-baseline status will be summarized.

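### The ESS table of subjects scoring 10 or more and 18 or more takes no account of baseline category, so it shows net prevalence and dilutes new-onset sleepiness

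*SAP*

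**What the plan says.** SAP 3.2.2 defines the categories on the total score: "A score of 10 or more is considered sleepy, and a score of 18 or more is very sleepy". SAP 5.14.2 then plans four kinds of ESS output.

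- Descriptive summaries: "The ESS individual questions and total score and corresponding changes from baseline will be summarized by treatment group and study visit".
- The categorical summary at issue: "The percentage of subjects with sleepy (10 or more) and very sleepy (18 or more) scores will also be summarized".
- A model: "The ESS total score will also be analyzed using the same method (MMRM analysis) described in" SAP 5.9.2, with a plot of LSMean change.
- A subject listing of item and total scores.

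SAP 5.14 places all safety analyses on the full analysis set, that is, every randomized subject who took at least one dose. Protocol 9.4.2 adds only this: "The C-SSRS, ESS, QUIP-RS, laboratory data, vital sign data, and ECG data will be summarized with descriptive statistics".

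Neither document defines a treatment-emergent ESS category. Neither says whether the percentage is by visit or at any time after baseline. Protocol 5.1 and 5.2 contain no ESS criterion. The schedule in Protocol 1.3 has ESS at Baseline and at every treatment visit from Week 2 to Week 27.

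**The concern.** A subject who enters with an ESS of 12 and stays there is counted in the same cell as one who goes from 4 to 12 on treatment. A percentage at or above 10 mixes the two. If it is shown by visit, new cases and resolved cases also cancel, so only the net prevalence is visible.

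The SAP refers to baseline in its other categorical safety summaries. For laboratory data, "Shift table will be used to summarize shifts from baseline toxicity grades to greatest (worst) treatment-emergent laboratory toxicity grade". For the C-SSRS, treatment-emergent ideation requires an increase from baseline (SAP 9.3). Supine blood pressure (5.14.6.1) and QTcF (5.14.7) pair absolute cut-offs with change-from-baseline categories. The ESS has neither.

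ESS is a listed safety endpoint. Protocol 2.1 names the effects linked to D2/D3 agonists that tavapadon aims to reduce: "notably, dose-limiting hypotension, impulse control disorders, sleep disorders, and, potentially, some forms of hallucinations". Protocol 8.3.1 also gives a score of 10 or more a practical meaning, since medical attention may be needed. How many subjects newly reach that score on each arm is therefore a natural safety question, and no planned table answers it directly.

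**Working it through.** The documents state no ESS rate and no ESS sample size, so there is no figure to reproduce. The size of the effect can only be illustrated.

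**Inputs.** From the documents: 174 subjects per group (Protocol 9.2) and the cut-off of 10 (SAP 3.2.2). Assumed: *p0*, the share at or above 10 at baseline (0% to 40%); *s*, the share of those still at or above 10 on treatment (100% or 80%, equal across arms); *i*, the new-onset rate among subjects below 10 at baseline.

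**Formula.** Percentage in the planned table = p0·s + (1 − p0)·i. With equal *s*, the first term cancels between arms:

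difference in the planned table = (1 − p0) × (i on tavapadon − i on placebo).

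**New onset 5% on placebo, 12% on tavapadon, s = 100%.** At p0 = 20%, placebo is 0.20 + 0.80 × 0.05 = 24.0% and tavapadon is 0.20 + 0.80 × 0.12 = 29.6%. The difference is 0.80 × 7.0 = 5.6 points.

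| p0 | Placebo | Tavapadon | Difference (points) | Ratio |
|---|---|---|---|---|
| 0% | 5.0% | 12.0% | 7.0 | 2.40 |
| 10% | 14.5% | 20.8% | 6.3 | 1.43 |
| 20% | 24.0% | 29.6% | 5.6 | 1.23 |
| 30% | 33.5% | 38.4% | 4.9 | 1.15 |
| 40% | 43.0% | 47.2% | 4.2 | 1.10 |

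Among subjects below 10 at baseline the contrast is 7.0 points and ratio 2.40 whatever *p0* is. With *s* = 80% and p0 = 20% the planned table gives 20.0% and 25.6% (5.6 points, ratio 1.28). With new onset of 10% and 20%, s = 100% and p0 = 20%, it gives 28.0% and 36.0% (8.0 points, ratio 1.29, against 10.0 points and 2.00).

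**Precision, for a smaller effect.** Take new onset of 5% and 10%, s = 80%, p0 = 20%.

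- Planned table, 174 per arm: 20.0% and 24.0%. SE = √[(0.20 × 0.80 + 0.24 × 0.76)/174] = 4.4 points, so the 95% half-width is 8.7 points and z = 4.0/4.4 = 0.90.
- Subjects below 10 at baseline, about 174 × 0.80 = 139 per arm: 5% and 10%. SE = √[(0.05 × 0.95 + 0.10 × 0.90)/139] = 3.1 points, so the half-width is 6.2 points and z = 1.59.

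**Nominal power** (two-sided 0.05, p0 = 20%, s = 100%), used only as a yardstick because no test of this percentage is planned: 0.22 in the planned table against 0.55 in the at-risk subset for 5% and 12%; 0.36 against 0.65 for 10% and 20%.

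**Cut-off of 18.** The same formula applies, with *p0* the share at or above 18 at baseline. If few subjects enter at that level, the dilution is small.

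**The case against.** The case on the other side has five parts.

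1. The SAP does not say in words that baseline cases are counted. That follows from absolute cut-offs and the absence of any restriction. Because the preceding sentence sets the display by group and visit, a by-visit table is the natural reading, and it would probably include baseline. A reader could then see the net change in prevalence. This stands, but net change still does not count new cases.
2. Other outputs address sleepiness. The MMRM includes the baseline score as a covariate, change from baseline is summarized by visit, and sleepiness reported as an adverse event enters the TEAE tables (SAP 5.14.1). A reader might infer that the trial could miss a real increase in sleepiness; these outputs are why the documents do not support that. They do not, however, show how many subjects crossed a cut-off.
3. Every rate above is assumed. A reader might infer that baseline cases dominate the table; nothing in the documents shows this, and at 0% baseline prevalence there is no dilution.
4. The ratio exaggerates the loss. In the 5% and 10% example the risk difference moves only from 5.0 to 4.0 points, and z in the at-risk subset is still below 1.96. This stands: the gain is in clarity and some precision.
5. Loss of subjects who stop early is partly covered, because the Week 27 assessments, including ESS, are done at premature discontinuation (Protocol 1.3, footnote b) and assigned to a visit window (SAP 4.2). They remain absent from later visits.

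**Conclusion.** The point holds as a loss of contrast in one descriptive safety table. SAP 5.14.2 does not separate subjects who were already sleepy at entry from those who become so on treatment, and no other planned ESS output counts the latter. With equal persistence across arms, the risk difference shrinks by the factor (1 − baseline prevalence), and the ratio shrinks more. The actual size is unknown because the documents give no baseline ESS distribution; over the assumed 10% to 40%, a 7.0-point difference in new onset shows as 6.3 to 4.2 points.

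It is not bias in favour of one arm: randomization should balance baseline sleepiness. If tavapadon also changed persistence among those already sleepy, the planned percentage would mix that effect with new onset, which is a reason to show both. Nor does the point bear on superiority to D2/D3 agonists, since the protocol states an aim and the trial has no such comparator.

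**What to change.** In SAP 5.14.2 add, by arm:

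- a shift table of baseline ESS category (below 10, 10 to 17, 18 or more) by worst on-treatment post-baseline category, using all assessments including early-termination and unscheduled ones, because SAP 4.2 otherwise keeps one value per window;
- from it, the number and percentage newly at 10 or more, and newly at 18 or more, among full-analysis-set subjects below that cut-off at baseline with at least one post-baseline ESS, with a 95% CI for each dose minus placebo.

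Keep the threshold percentages, state that they are by visit, and include a baseline column. The shift table also shows movement from 10–17 to 18 or more, which a new-onset rate at 10 alone would omit.

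The cost is a short SAP addition and one or two tables from data already collected; no efficacy analysis changes. There are two downsides. The new-onset rate has a smaller denominator (about 139 of 174 per arm if 20% are at or above 10 at baseline). An any-visit rate also gives fewer chances to record a case in an arm with more early discontinuation, so report it next to the number of ESS assessments or the exposure in each arm.
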